### **3.4.2. Baseline characteristics**

Baseline characteristics (including demographics, physical measurements, disease history and prior anti-cancer therapies) are described in Section 6.5.1. These baseline characteristics are not planned to be included as stratification variables or covariates in statistical models unless otherwise specified in Section 6.

## **3.5. Safety Endpoints**

### **3.5.1. Adverse events**

#### **Treatment-Emergent Adverse Events**

Treatment-emergent adverse events (TEAEs) are those events with onset dates occurring during the on-treatment period for the first time, or if the worsening of an event is during the on-treatment period.

**On-treatment period** is defined as the time from the first dose of study treatment through minimum (30 days + last dose of study treatment, start day of new anti-cancer drug therapy – 1 day). The start day of new anti-cancer drug therapy after the first dose of study treatment is derived as outlined in Section 5.2.5.

#### **Adverse Events of Special Interest (AESIs)**

AESIs are immune-related adverse events (irAE) and infusion-related reactions (IRRs). The criteria for classification of an AE as an irAE or IRR are described in Appendices 1 and 2, respectively.

## **4. ANALYSIS SETS**

Data for all patients will be assessed to determine if patients meet the criteria for inclusion in each analysis population prior to releasing the database and classifications will be documented per Pfizer's standard operating procedures.

Only patients who signed informed consent will be included in the analysis sets below.

#### **4.1. Full Analysis Set**

For the randomized phase: The full analysis set (FAS) will include all randomized patients. Patients will be classified according to the study treatment assigned at randomization.

For the non-randomized phase: The FAS will include all patients who receive at least one dose of study drug. Patients will be classified according to the study treatment actually received. If a patient receives more than one study treatment the patient will be classified according to the first study treatment received.

#### **4.2. Safety Analysis Set**

For the randomized phase: The safety analysis set will include all patients who receive at least one dose of study drug. Patients will be classified according to the study treatment assigned at randomization unless the incorrect treatment(s) was/were received throughout the dosing period in which case patients will be classified according to the first study treatment received.

For the non-randomized phase: The safety analysis set will include all patients who receive at least one dose of study drug. Patients will be classified according to the study treatment actually received. If a patient receives more than one study treatment, the patient will be classified according to the first study treatment received. In the non-randomized phase of the study, the FAS and the safety analysis set are identical.

#### **4.3. Other Analysis Set**

##### **4.3.1. DLT-evaluable set**

The DLT-evaluable set includes all enrolled patients during the dose-finding phase who:

- receive at least 1 dose of avelumab and axitinib, and
- either experience DLT during the first 2 cycles of combination axitinib + avelumab treatment, or complete the primary DLT observation period for the first 2 cycles of combination treatment (4 weeks).

Patients who withdraw from study treatment before receiving at least 75% of the planned first 2 cycles of axitinib starting from Cycle 1 Day 1 after completion of the Lead-in PK period or 2 infusions of avelumab within the primary DLT observation period due to reasons other than investigational product-related adverse events are not evaluable for DLT.

This analysis set will be used only in the Dose-finding phase of the study for determination of MTD/RP2D.

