Number of Toxicities	0	E	E	E	E	E	E
	1	D	S	S	S	S	E
	2		DU	D	S	S	S
	3			DU	DU	D	D
	4				DU	DU	DU
	5					DU	DU
	6						DU

E = Escalate to the next higher dose

S = Stay at the current dose

D = De-escalate to the next lower dose

U = The current dose is unacceptably toxic

Note: for the initial dose level (ie, “DL1”) evaluated, the doses are maintained (“S”), while DL-1A or DL-1B may be escalated (“E”).

As an example, if the total number of patients treated at DL1 is 3, the following dosing rules are applied:

- 0 - 1 DLTs → remain at the same dose (DL1);
- 2 DLTs → de-escalate to DL-1 and allow for possible escalation back to DL1;
- 3 DLTs → de-escalate to DL-1 and consider DL1 as intolerable.

If the dose is de-escalated to DL-1A and DL-1B and the total number of patients then treated at DL-1A and DL-1B is 3, the following dosing rules are applied within each dose level:

- 0 DLTs (in DL-1A and DL-1B) → escalate back to DL1;
- 1 DLT (in either DL-1A or DL-1B) → remain at the same DL (DL-1);
- 2-3 DLTs (in either DL-1A or DL-1B) → de-escalation not possible and depending on the distribution of the DLTs one or both doses at DL-1 will be considered intolerable.

Rules for dose-finding, using the mTPI method, include the following:

- The target enrollment cohort size is 3 patients. However, patients may be enrolled in cohort sizes of 3-4 depending on the number of potential patients identified at participating sites. The patients treated at each dose level may initiate dosing simultaneously. If the first 2 patients experience a DLT prior to enrollment of the third one, the dose level will be deemed intolerable and the dose level will be de-escalated.

090177e1907c3de0\0.1\Draft\Versioned On:01-Mar-2019 17:22 (GMT)

- The next cohort may be enrolled when all patients at the current dose cohort have been evaluated for 4 weeks (ie, the first 2 treatment cycles), or experience a DLT, whichever comes first.
- If a patient withdraws from study treatment before receiving at least 75% of the planned first 2 cycles of axitinib or 2 infusions of avelumab for reasons other than study drug-related toxicity, another patient will be enrolled to replace that patient at the current dose level.

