9.1. Analysis Sets

The following patient sets will be assessed:

- Full Analysis Set.

The full analysis set includes all patients who receive at least 1 dose of study drug (axitinib or avelumab) and all patients who are randomized independent of whether they received a dose of study drug. Patients will be classified according to the treatment actually received or according to the treatment assigned at randomization if randomization occurs in this study.

- Safety Analysis Set.

The safety analysis set includes all enrolled patients who receive at least 1 dose of avelumab or axitinib.

- Per Protocol Analysis Set (Dose Finding Phase; evaluable for DLT).

The per protocol analysis set includes all enrolled patients during the Dose Finding Phase who:

- Receive at least 1 dose of avelumab and axitinib; and
- Either experience DLT during the first 2 cycles of combination axitinib + avelumab treatment, or complete the primary DLT observation period for the first 2 cycles of combination treatment (4 weeks).

Patients who withdraw from study treatment before receiving at least 75% of the planned first 2 cycles of axitinib starting from Cycle 1 Day 1 after completion of the Lead-in PK period or 2 infusions of avelumab within the primary DLT observation period due to reasons other than investigational product-related adverse events are not evaluable for DLT.

- PK Analysis Set.

The PK analysis set is defined as all enrolled patients who receive at least 1 dose of avelumab or axitinib and who have at least 1 concentration above the below limit of quantitation (BLQ) of either study drug.

The PK parameter analysis set is defined as all enrolled patients who receive at least 1 dose of avelumab or axitinib and who have at least 1 of the PK parameters of interest of either study drug.

- Immunogenicity Analysis Set.

The immunogenicity analysis set is defined as all enrolled patients who receive at least 1 dose of avelumab or axitinib and who have at least 1 ADA sample collected.

- Biomarker Analysis Set.

The biomarker analysis set is defined as all enrolled patients who have at least one screening biomarker assessment and who receive at least 1 dose of avelumab or axitinib. Analysis sets will be defined separately for blood-based and tumor tissue-based biomarkers.

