    - Single laboratory values out of normal range that are unlikely related to trial treatment according to the investigator, do not have any clinical correlate, and resolve to Grade  $\leq 1$  within 7 days with adequate medical management are not to be considered DLTs.
  - Inability to complete at least 75% of the first 2 cycles doses of axitinib (starting from Cycle 1 Day 1 after completion of the Lead-in PK period) or 2 infusions of avelumab within the DLT observation period due to investigational product-related toxicity.

In absence of associated clinical abnormalities, abnormal laboratory tests should be repeated to confirm relevance. While the rules for adjudicating DLTs in the context of dose finding/dose expansion phases are specified above, an AE not listed above, or an AE meeting the DLT criteria above but occurring outside of the DLT observation period may be defined as a DLT after consultation between sponsor and investigator, based on the emerging safety profile.

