The 3 dosing intervals are associated with 3 different dose-escalation decisions. The under-dosing interval corresponds to a dose escalation (E), over-dosing corresponds to a dose de-escalation (D), and proper-dosing corresponds to remaining at the current dose (R). Given a dosing interval and a probability distribution, the unit probability mass (UPM) of that dosing interval is defined as the probability of a patient belonging to that dosing interval divided by the length of the dosing interval. The mTPI design calculates the UPMs for the 3 dosing intervals, and the one with the largest UPM informs the corresponding dose-finding decision, which is the dose level to be used for future patients. For example, if the under-dosing interval has the largest UPM, the decision will be to escalate, and the next cohort of patients will be treated at the next higher dose level. Ji and collaborators have demonstrated that the decision based on UPM is optimal in that it minimizes a posterior expected loss (ie, minimizes the chance of making a wrong dosing decision).

The dose finding phase of the trial uses a modified version of the mTPI design that maximizes the number of evaluable patients treated at each dose level at 6. Dose finding is completed when 6 DLT-evaluable patients have been treated at the highest dose with a DLT rate  $< 0.33$ .

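### The exposure minimum for DLT evaluability applies only to patients who withdraw, so a patient who is under-dosed for non-toxicity reasons but stays on treatment counts, read literally, as DLT-free

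*SAP*

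**What the plan says.** - **Entry to the set.** SAP 4.3.1 takes dose-finding patients who "receive at least 1 dose of avelumab and axitinib, and" then either have a DLT in the first two combination cycles "or complete the primary DLT observation period for the first 2 cycles of combination treatment (4 weeks"). SAP 3.1 ends that window at the planned date of the third avelumab dose, so it is a calendar limit.
- **Exclusion from the set.** "Patients who withdraw from study treatment before receiving at least 75% of the planned first 2 cycles of axitinib", or 2 infusions of avelumab, "due to reasons other than investigational product-related adverse events are not evaluable for DLT".
- **Protocol 9.1** has the same trigger: "Patients who withdraw from study treatment before receiving at least 75% of the planned first 2 cycles of axitinib starting from Cycle 1 Day 1".
- **Replacement, Protocol 3.1.1.2.** The rule opens "If a patient withdraws from study treatment before receiving at least 75% of the planned first 2 cycles of axitinib", so it too requires withdrawal.
- **Toxicity route.** Under SAP 3.1 and Protocol 3.1.2, failing the same minimum "within the DLT observation period due to investigational product-related toxicity" is itself a DLT.
- **Use of the set.** SAP 5.1.2: "Dose finding is completed when 6 DLT-evaluable patients have been treated at the highest dose with a DLT rate" below 0.33. Protocol 3.2 defines the MTD by DLTs in under 33% of DLT-evaluable patients.
- **Status.** SAP 6 records that dose finding was complete by SAP V2, with only DL1 tested.

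**The concern.** The plan treats one and the same exposure shortfall in three ways, depending on its cause and on whether the patient stays on treatment:

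| Below 75% of axitinib or 2 infusions because of | Patient | Status |
|---|---|---|
| product-related toxicity | either | DLT |
| another reason | withdraws | not evaluable, replaced |
| another reason | stays on treatment, no DLT | evaluable, DLT-free |

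The first two rows show that the sponsor regards this exposure as necessary for judging tolerability. The third row does not require it. The discretion in SAP 3.1 and Protocol 3.1.2 to reclassify events can add DLTs, but it does not take an under-dosed patient out of the denominator.

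The rate in this set is the primary endpoint. A patient with reduced opportunity to show a DLT pulls it down and fills one of the 6 places that end dose finding.

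The planned outputs would not reveal the problem. SAP 6.5.3 summarizes exposure by cycle for avelumab only, and axitinib only overall.

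**Working it through.** **1. Reproduce Table 3.** Inputs: the stated target interval (0.25, 0.33) from Protocol 9.2.1 and the decision cells for n = 1 to 6. Two assumptions are not in the documents: a Beta(1,1) prior, and U when P(p > 0.33 | data) > 0.95. Unit probability mass (UPM) = posterior probability of an interval ÷ its length, and the largest decides. All 27 of 27 cells match. (The stated offsets, 0.33 − 0.05 and 0.33 + 0.03, give (0.28, 0.36) instead. That is a separate matter; it changes only the 3/6 cell.)

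The two cells that matter here, with F the posterior distribution function:

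- 2 DLTs in 3, Beta(3,2), F(p) = 4p³ − 3p⁴: F(0.25) = 0.0508, F(0.33) = 0.1082. UPMs: under 0.0508/0.25 = 0.20; proper (0.1082 − 0.0508)/0.08 = 0.72; over (1 − 0.1082)/0.67 = 1.33. Decision **D**.
- 2 DLTs in 4, Beta(3,3), F(p) = 10p³ − 15p⁴ + 6p⁵: F(0.25) = 0.1035, F(0.33) = 0.2050. UPMs: 0.1035/0.25 = 0.41; (0.2050 − 0.1035)/0.08 = 1.27; (1 − 0.2050)/0.67 = 1.19. Decision **S**.

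**2. Decisions that change when one counted patient is uninformative.** Compare x/n with x/(n − 1):

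| As counted | Informative only |
|---|---|
| 1/2 = S | 1/1 = D |
| 2/3 = D | 2/2 = DU |
| 2/4 = S | 2/3 = D |
| 3/5 = D | 3/4 = DU |
| 1/6 = E | 1/5 = S |

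Every change is in the less cautious direction. The last has no effect at DL1, where the Table 3 note maintains the dose.

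**3. Can the case arise without withdrawal?** Planned axitinib is 28 days × 2 = 56 doses, and 75% is 42. Protocol 5.7.3 describes stopping at least 24 hours before a procedure and resuming 7 days after minor surgery. Taking both, with the gap inside the window, 8 days × 2 = 16 doses are missed and 40/56 = 71.4% remain. The 24-hour stop is worded for major surgery or an interventional procedure. Without it, 42/56 = 75.0% just meets the minimum. For major surgery, 15 to 22 days off leaves 26/56 = 46% to 12/56 = 21%. Avelumab is also to be delayed for surgery. None of this requires withdrawal.

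**4. Effect on the <33% rule at 6 patients.** 1/6 = 16.7% meets it; 2/6 = 33.3% does not. So the rule needs at most 1 DLT. With k uninformative, DLT-free patients and m = 6 − k:

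P(at most 1 DLT) = (1 − p)^m + m·p·(1 − p)^(m−1)

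At p = 0.33:
- k = 0: 0.67⁶ + 6 × 0.33 × 0.67⁵ = 0.0905 + 0.2673 = 35.8%
- k = 1: 0.67⁵ + 5 × 0.33 × 0.67⁴ = 0.1350 + 0.3325 = 46.8%

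| True rate | k = 0 | k = 1 | k = 2 |
|---|---|---|---|
| 0.33 | 35.8% | 46.8% | 59.9% |
| 0.40 | 23.3% | 33.7% | 47.5% |
| 0.50 | 10.9% | 18.8% | 31.3% |

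The expected observed rate shrinks by the factor (6 − k)/6, for example 0.33 × 5/6 = 0.275.

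**5. Partial exposure.** The k = 1 and k = 2 columns give the under-dosed patient no DLT risk at all. If one such patient keeps half the risk (0.165, an illustrative assumption), the figure at p = 0.33 is 0.835 × 0.4675 + 0.165 × 0.1350 = 41.3%. With full risk it returns to 35.8%.

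**The case against.** - **Completing two cycles of combination treatment may be meant to imply adequate dosing.** On that reading a patient with one infusion would not qualify. The wording allows this, but it states no threshold, gives the period as 4 weeks, and ends it on a planned date. The ambiguity stands; it does not close the gap.
- **The remaining group is narrow.** Toxicity-driven shortfall is a DLT, and non-toxicity withdrawals are excluded and replaced. Diaries, tablet counts and a Cycle 1 Day 5 contact (Protocol 5.2) monitor adherence. This is fair, and it limits how often the gap matters.
- **A reader might infer that an under-dosed patient could not have a DLT.** The documents do not support that. DLTs count if attributable to either drug, so a partly dosed patient is partly informative. This is why the figures for uninformative patients are upper bounds.
- **A reader might infer that removing one patient from 6 would overturn the MTD call.** Simple fractions do not show it: 1/6, 1/5 and 1/4 all fall below 33%, while 2/6 (33.3%) and 2/5 (40%) both fail. The effect lies in the probability of reaching a passing count and in the Table 3 cells above.
- **The RP2D does not rest on this rate alone.** It is confirmed in expansion using all safety, efficacy and PK data (Protocol 3.1.1.2) and may be set below the MTD (Protocol 3.4). This stands, and it reduces the consequence for the final dose choice.
- **Redefining the set now is post hoc.** This is correct, and it determines the form of the remedy.

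**Conclusion.** The gap is real on the literal text of both documents. It can bias the DLT rate downward, and every Table 3 decision that it changes becomes less cautious. One uninformative patient among 6 raises the chance of meeting the <33% rule at a true rate of 0.33 by up to 11 percentage points (35.8% to at most 46.8%).

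This rests on three assumptions: independent patients with a common DLT risk, an under-dosed patient with no risk (hence an upper bound), and the literal reading of what it means to complete the window.

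A reader might go further and conclude that the reported DLT rate is diluted or that DL1 was wrongly accepted. The documents do not support either conclusion: they do not show that such a patient occurred. Past allocation cannot change, but the DLT table in SAP 6.1.1 is still a planned output, and its denominator should be defensible.

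**What to change.** **Wording.** Define DLT-evaluable as having had a DLT, or having completed the window with at least 75% of planned axitinib and 2 avelumab infusions, whether or not the patient withdrew. Align Protocol 9.1 and the replacement rule in Protocol 3.1.1.2.

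**Analysis, given that dose finding is complete.**
- List Cycle 1-2 axitinib and avelumab exposure for each DLT-evaluable patient, counting axitinib from Cycle 1 Day 1 so that the lead-in is left out.
- Report the DLT rate under the exposure-based definition beside the rate under the current one.
- State whether at least 6 patients remain.

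**Cost.** One listing, one extra row in the DLT table, and wording changes in both documents. The exposure data are already collected. Protocol 9 and SAP 2 require a protocol amendment for a major change to the primary endpoint or its analysis; keeping the current definition as primary and adding the re-analysis beside it may limit that. The denominator may fall below 6 with no dose-finding cohort left to refill it, and the re-analysis is post hoc and should be labelled so. If no patient is affected, the listing confirms the result.

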##### **4.3.2. PK analysis set**

The PK concentration analysis set is a subset of the safety analysis set and will include patients who have at least one post-dose concentration measurement above the lower limit of quantitation (LLQ) for avelumab or axitinib.

The PK parameter analysis set is a subset of the safety analysis set and will include patients who have at least one of the PK parameters of interest for avelumab or axitinib.

#### **4.3.3. Biomarker analysis set**

The biomarker analysis set for biomarkers that are measured only at screening is a subset of the safety analysis set and will include patients who have at least one screening biomarker assessment.

The biomarker analysis set for biomarkers that are measured sequentially is a subset of the safety analysis set and will include patients who have at least one screening and one on-treatment biomarker assessment for the same marker.

Analysis sets will be defined separately for blood-based and tumor tissue-based biomarkers.

#### **4.3.4. Immunogenicity analysis set**

The immunogenicity analysis set is a subset of the safety analysis set and will include patients who have at least one ADA/nAb sample collected for avelumab.

### **5. GENERAL METHODOLOGY AND CONVENTIONS**

#### **5.1. Hypotheses and Decision Rules**

##### **5.1.1. Hypotheses and sample size determination**

###### **Dose-finding phase**

There is no formal hypothesis testing planned for this study. The objective of the dose-finding phase is to determine MTD or RP2D.

Due to the dynamic nature of the dose allocation procedure and unknown safety profile of the combination, the sample size using mTPI approach (see Section 5.1.2 for details) cannot be determined in advance. It is expected that approximately 15 DLT-evaluable patients will be required for the dose-finding phase based on the mTPI method.

Based on the emerging PK data and after the completion of the dose-finding phase of study based on the mTPI method, it may be necessary to enroll up to 8 additional patients to further assess the effect of avelumab on the PK of axitinib. These additional patients will be treated concurrently with the initiation of the dose-expansion phase.

###### **Dose-expansion phase**

Up to approximately 40 patients will be included in the dose-expansion phase of the study for each MTD dose level cohort expanded. A sample size of 40 patients will provide at least 90% probability to observe at least 1 AE if the true incidence of the AE in the population is  $\geq 6\%$ .

It is expected that at most approximately 55 patients will be enrolled to achieve all study objectives.

## 5.1.2. Decision rules

### Dose-finding phase

Many alternative designs have been proposed to the standard 3+3 design for Phase 1 dose escalation trials that improve accuracy, efficiency and statistical validity.

The modified toxicity probability interval (mTPI) design is an interval-type of design that uses a Bayesian statistics framework and a beta/binomial hierarchical model to compute the posterior probability of 3 dosing intervals that reflect the relative difference in probability between the toxicity rate of each dose level to the target rate ( $p_T = 0.33$ ). If the toxicity rate of the currently used dose level is far smaller than  $p_T$ , the mTPI will recommend escalating the dose level; if it is close to  $p_T$ , the mTPI will recommend continuing at the current dose; if it is far greater than  $p_T$ , the mTPI will recommend de-escalating the dose level. These rules are conceptually similar to those used by the 3+3 design, except the decisions of an mTPI design are based on posterior probabilities calculated under a coherent probability model.

Being a model-based design, mTPI automatically and appropriately tailors dose-escalation and de-escalation decisions for different trials with different toxicity parameters. More importantly, all the dose-escalation decisions for a given trial can be pre-calculated under the mTPI design. Thus, compared to other advanced model-based designs published in the literature, the mTPI design is logistically less complicated and easier to implement.

Decision rules are based on calculating unit probability mass (UPM) of 3 dosing intervals corresponding to under, proper, and over dosing in terms of toxicity. Specifically, the underdosing interval is defined as  $(0; p_T - e_1)$ , the over-dosing interval  $(p_T + e_2)$ , and the proper-dosing interval  $(p_T - e_1, p_T + e_2)$ , where  $e_1$  and  $e_2$  are small fractions. Based on the safety profile of avelumab as a single-agent in Study EMR100070-001,  $e_1$  is selected as 0.05, and  $e_2$  is selected as 0.03. Therefore, the target dosing interval for the DLT rate is  $(0.25, 0.33)$ .

The 3 dosing intervals are associated with 3 different dose-escalation decisions. The under-dosing interval corresponds to a dose escalation (E), over-dosing corresponds to a dose de-escalation (D), and proper-dosing corresponds to remaining at the current dose (R). Given a dosing interval and a probability distribution, the unit probability mass (UPM) of that dosing interval is defined as the probability of a patient belonging to that dosing interval divided by the length of the dosing interval. The mTPI design calculates the UPMs for the 3 dosing intervals, and the one with the largest UPM informs the corresponding dose-finding decision, which is the dose level to be used for future patients. For example, if the under-dosing interval has the largest UPM, the decision will be to escalate, and the next cohort of patients will be treated at the next higher dose level. Ji and collaborators have demonstrated that the decision based on UPM is optimal in that it minimizes a posterior expected loss (ie, minimizes the chance of making a wrong dosing decision).

The dose finding phase of the trial uses a modified version of the mTPI design that maximizes the number of evaluable patients treated at each dose level at 6. Dose finding is completed when 6 DLT-evaluable patients have been treated at the highest dose with a DLT rate  $< 0.33$ .

